Therefore, the issue that requires investigation is the effect of the in-line filter on the gas exchange measurements, as these are the ultimate 'product' of the CPET testing. If these values are severely affected ($> 5\%$) by an inline filter, then other mitigation strategies may need to be considered.

Further, we need to establish the effects of the in-line filter on several of the common CPET hardware/software platforms in use throughout the world (e.g Medical Graphics Corporation, Vyair Vmax, Cosmed, etc), specifically on the important measured variables (V_E , VO_2 , VCO_2 and HR). We also want to evaluate the effects of the filter on reducing particle concentrations that are generated by subjects during CPET, as well as the time that is required to clean the room air.

Acquiring this data and publishing it in the near future would be important to safely return to practice and also to support our CPET colleagues throughout the world.

Methods

1. Inclusion and Exclusion Criteria

Inclusions:

- Ages 18-65, Male or Female

- Normal exercise tolerance without dyspnea or clinically important limitation of exercise tolerance.

Exclusions:

- Complicated heart or lung disease
- Pregnancy
- Complex arrhythmias
- Severe Anemia
- Uncontrolled Diabetes, hypertension, or untreated thyroid disease
- Has any of the following symptoms in the last 21 days: sore throat, cough, chills, body aches for unknown reasons, shortness of breath for unknown reasons, loss of smell, loss of taste, fever at or greater than 100 degrees Fahrenheit.
- COVID-19 test positive within 21 days.
- Any Disease that the PI feels will markedly increase the risk of CPET testing

2. Sample size: 10 subjects

3. Subject recruitment:

Advertisement will be posted in the public area at Rush University Medical Center, including fitness center, healthy subjects including employee or patients/family in Rush University Medical Center will be recruited.

4. Study Timelines

- *The duration of an individual subject's participation in the study.*

This requires two visits over two days for an hour or less on each visit. Two increment work rate CPET studies with one performed on each day taking no

more than 45 minutes. With a one-hour break for cleaning and room air exchange between subjects.

- *The duration anticipated to enroll all study subjects.*
3 weeks (to prescreen and set up testing schedule)
- *The estimated date for the investigators to complete this study (complete primary analyses)*

August 2020

5. Study outcome

- Primary: Determine the effect of the in-line filter (< 5% effect or > 5% effect) on minute ventilation (V_E), oxygen uptake (VO_2), carbon dioxide output (VCO_2), and heart rate (HR) during CPET. Effect of in line filter on oxygen pulse, ventilatory equivalents, end tidal O_2 and CO_2 . Sensation of dyspnea by the subject (Borg Score).
- Secondary: Effect of in line filter on aerosol particle concentrations inside the test room during CPET testing to determine if wait time between patients can be calculated

6. Termination criteria:

Standard termination criteria for CPET during testing are BP > 240/120, serious arrhythmias, chest pain, oxygen desaturation and severe dyspnea.

7. Procedures Involved*

- **study design.**

The subject will spend two visits one hour each day (~ 1 hour) in the PFT lab and will have two separate CPET (Vyair Vmax, Vyaire medical, Mettawa, IL)

tests performed by registered pulmonary function technologists. One day the test will be performed with the inline filter during CPET, and the second day the CPET will be performed without a filter. During the test, electrocardiogram (ECG) electrodes will be attached to participants as well as a mask, and their heart rate will be measured for 10 minutes at rest, and then they will ride bicycle for 20 minutes at different levels of intensity. The work rate increment will be the same for both tests. All gas exchange and aerosol particle concentrations measures will be compared with Bland Altman analysis and paired t-testing.

- **Provide a description of all research procedures being performed and when they are performed, including procedures being performed to monitor subjects for safety or minimize risks.**

The standard CPET (Wasserman 2012) includes real time monitoring of the 12 lead EKG, pulse oximetry, gas exchange variables, physician assessment, and symptom query.

- **Procedures performed to lessen the probability or magnitude of risks.**

- *All drugs and devices used in the research and the purpose of their use, and their regulatory approval status.*

No drugs. The device is an inline filter (MicroGard™ II PFT Filter).

MicroGard™ II PFT Filter

Proposed filter to be used (current standard of care with PFTs)

MicroGard™ II PFT Filter in line with Mouthpiece and Flow Sensor

** Picture shows the Pitot flow sensor, and adapter, the Microgard Filter, and a standard mouthpiece.

- The relevant characteristics of this filter are:

Inspiratory Resistance: 0.45 cm/H₂O/L/S

Expiratory Resistance: 0.45 cm/H₂O/L/S

Filter Efficiency: Bacteria>99.98%

Virus filtering efficiency > 99.92%

Dead Space = 53ml

The filter is for single patient and single occasion use only.

8. Data Management* and Confidentiality

- Describe the data analysis plan, including any statistical procedures.**

Data from each subject will be compared with a Bland Altman Analysis

(<https://www.jstor.org/stable/2987937?seq=1>) and paired T-Testing using the non-filter data for minute ventilation (VE), oxygen uptake (VO₂), carbon dioxide output (VCO₂), and heart rate (HR) during a work rate increment CPET, comparison of the non-filter to the filter data will be analyzed. Mean and standard deviation of the measurements will be presented. Statistical importance will be assigned at P ≤ 0.05.

- Describe the steps that will be taken to secure the data (e.g., training, authorization of access, password protection, encryption, physical controls, certificates of confidentiality, and separation of identifiers and data) during storage, use, and transmission.**

No identification will be collected. The electronic data will be stored on the Redcap, which is a secure network with appropriate institutional security, and password protection.

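### No random or balanced order is set for the filter and no-filter tests; if all 10 subjects do the filter test first, the day effect cannot be separated from the filter effect.

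*Combined protocol and SAP*

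**What the plan says.** Methods section 4 (Study Timelines) gives the visit structure: "This requires two visits over two days for an hour or less on each visit". One exercise test is done on each day. The study design paragraph of section 7 assigns the conditions to the days: "One day the test will be performed with the inline filter during CPET, and the second day the CPET will be performed without a filter". Section 2 gives the number of subjects: "Sample size: 10 subjects".

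The one feature stated to be equal across a subject's two tests is the exercise load: "The work rate increment will be the same for both tests". The one-hour break for cleaning and air exchange in section 4 falls between subjects, not between the two conditions.

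For analysis, section 7 says: "All gas exchange and aerosol particle concentrations measures will be compared with Bland Altman analysis and paired t-testing". Section 8 adds that "comparison of the non-filter to the filter data will be analyzed", and then: "Statistical importance will be assigned at P ≤ 0.05". Neither section includes a day, period or sequence term. Random order, counterbalancing, alternation, a familiarisation test and a set interval between visits are not mentioned anywhere.

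**The concern.** Every within-subject contrast in this trial is also a contrast between two days. Subjects may respond differently at a second test for reasons unrelated to the filter, such as getting used to the mask and the bicycle. If everyone has the filter on the same day, that change is counted as filter effect.

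The primary outcome in section 5 is a narrow one: whether the effect on VE, VO2, VCO2 and HR is below or above 5%. The Background attaches a consequence to the answer. If gas-exchange values are affected by more than 5% "by an inline filter, then other mitigation strategies may need to be considered". A day effect of a few per cent could therefore make a filter that matters look harmless, or the reverse. The document gives no sign for either effect, and the sign may differ between the four variables.

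The Borg score is compared across the same two days and shares the problem. Room aerosol counts are also compared across days, but familiarisation does not apply to them. No size can be given for either.

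**Working it through.** **Inputs from the document:** 10 subjects; 2 visits with one test each; a 5% threshold; significance at P ≤ 0.05 (taken as two-sided). The plan has no sample-size or power figure to reproduce.

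**Assumed, not in the document:** a day effect of 1 to 3%; an SD of paired differences of 3, 4, 5, 8 or 10%; and, for steps 3 and 5, a decision rule that the observed mean lies inside ±5%.

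**Step 1: can day and filter be separated?** A model with 10 subject terms, one day term and one filter term has 20 observations and 12 columns. With all subjects filter-first the rank is 11, so one effect cannot be estimated. With 5 subjects in each order the rank is 12.

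**Step 2: bias.** Let *k* be the number tested with the filter first and *D* the day effect (day 2 minus day 1). Then

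mean(filter − no filter) = filter effect + *D* × (10 − 2*k*)/10.

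The multiplier is −1.0 at *k* = 10, −0.6 at 8, −0.4 at 7, −0.2 at 6 and 0 at 5. The sign reverses when no-filter-first is the majority.

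**Step 3: effect on the 5% question, all filter-first.** With a true effect of −6%, a 3% fall by day 2 gives an expected estimate of −6 + 3 = −3%, and a 3% rise gives −6 − 3 = −9%. The chance that the mean lies inside ±5% is Φ((5 − c)/SE) − Φ((−5 − c)/SE), where c is the expected estimate and SE = SD/√10:

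| Day effect | c | SD 3% | 4% | 5% | 8% | 10% |
|---|---|---|---|---|---|---|
| none | −6 | 15% | 21% | 26% | 35% | 38% |
| 3% fall | −3 | 98% | 94% | 90% | 78% | 73% |
| 3% rise | −9 | 0% | 0.1% | 0.6% | 6% | 10% |
| 1% fall | −5 | 50% | 50% | 50% | 50% | 50% |
| 1% rise | −7 | 2% | 6% | 10% | 21% | 26% |

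**Step 4: effect on the plan's own test, all filter-first.** For an inert filter, the chance that the paired t-test rejects zero comes from the noncentral t with 9 df and noncentrality |*D*|√10/SD. The nominal rate is 5%:

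| Day effect, either sign | SD 3% | 4% | 5% | 8% | 10% |
|---|---|---|---|---|---|
| 3% | 80% | 56% | 40% | 19% | 14% |
| 2% | 47% | 29% | 21% | 11% | 9% |
| 1% | 16% | 11% | 9% | 6% | 6% |

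**Step 5: order left to scheduling.** Take a filter-first majority, true effect −6%, SD 4% and a 3% day effect. The chance of a mean inside ±5% is 21% with no day effect. At 6:4 (c = −5.4 or −6.6) it becomes 38% with a fall or 10% with a rise. At 7:3 (c = −4.8 or −7.2) it is 56% or 4%. At 8:2 (c = −4.2 or −7.8) it is 74% or 1%. If order fell like a coin toss, the mean absolute multiplier would be 0.25, and a split of 7:3 or more uneven would have probability 0.34.

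**The case against.** **The wording is open to another reading.** The design sentence begins with one day, not the first day. It may mean one day and the other day, with the sequence left open. That stands: complete aliasing follows only from the literal reading. On the looser one, with coin-toss order, a 3% day effect shifts the estimate by 0.25 × 3, or about 0.7 points, on average. But nothing in the plan leads to 5:5, so order stays uncontrolled on either reading.

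**The sizes are assumed.** This also stands. The figures show sensitivity; they are not evidence that a day effect of this size exists. The aliasing under one fixed order needs no such assumption.

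**A true effect of −6% is close to the most sensitive point.** This is fair, since the hypothesis is an effect below 5%. With a true −1% and a 3% day effect, the expected estimate is −1 + 3 = +2% or −1 − 3 = −4%, both inside the threshold. At SD 4% the chance of a mean inside 5% goes from 99.9% to 99% or 78%. So if the filter effect is small, the expected answer does not flip. The trial is run because that is not known.

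**The same work rate increment removes one source of day-to-day difference.** It does, but it fixes the external load and not the subject's response on a second visit.

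**A 5:5 order is not a complete guarantee.** The bias is zero only if all 10 complete both visits and the day effect is additive and equal in both orders. With one dropout (5:4) the plain difference keeps (5 − 4)/9 = 1/9 of the day effect, or 0.33 points for a 3% effect.

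**Conclusion.** The concern holds and should be fixed before the first test. No random or balanced order is specified. If the design sentence is followed literally, day and filter effects are fully aliased for all four primary variables, and no later analysis can separate them. If order is left to scheduling, the bias is partial and proportional to the imbalance.

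The need to correct the plan rests on the text alone. The size of the bias rests on assumed day effects and SDs, and it can go in either direction. It matters most when the true filter effect is near 5%, where a day effect of 1 to 3% can change the answer to the primary question.

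**What to change.** **Essential.** State in the study design paragraph that order is allocated at random from a list prepared before enrolment, with 5 subjects filter-first and 5 no-filter-first. A balanced list is preferable to independent coin tosses, which give 8:2 or worse with probability 0.11. The cost is the list and one sentence, with no extra subjects, visits or tests.

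**Recommended in addition.** Estimate filter minus no-filter from a 2×2 crossover model with a period term, and report the 95% confidence interval. With complete 5:5 data the plain paired t-test is already unbiased for an additive day effect, so the term is a refinement; it also covers an uneven split after dropout.

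- *Cost:* one sentence in the analysis plan and one degree of freedom. The critical t goes from 2.262 (9 df) to 2.306 (8 df), a ratio of 1.019, so the interval multiplier is about 1.9% wider. With no day effect and an assumed SD of 5%, power for a 5% effect goes from 0.80 to 0.79.
- *Gain:* by simulation under 5:5 order with a 3% day effect, power for a 5% effect rises from 0.68 to 0.79 at SD 5%, and from 0.26 to 0.29 at SD 10%. At a 1% day effect and SD 5% it is 0.79 either way.

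### Bland-Altman analysis of 10 subjects is planned with no confidence interval for the mean difference or the limits of agreement, and the promised summary does not convey paired precision

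*Combined protocol and SAP*

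**What the plan says.** All references are to the combined protocol and SAP.

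- Methods, item 2: "Sample size: 10 subjects". No power, SD or precision basis is given.
- Section 7, study design: "One day the test will be performed with the inline filter during CPET, and the second day the CPET will be performed without a filter". Each subject therefore contributes one filtered and one unfiltered test.
- Section 7, study design: "All gas exchange and aerosol particle concentrations measures will be compared with Bland Altman analysis and paired t-testing".
- Section 8, data analysis plan, repeats the method ("Data from each subject will be compared with a Bland Altman Analysis", together with paired t-tests), then adds "Mean and standard deviation of the measurements will be presented" and "Statistical importance will be assigned at P ≤ 0.05".
- Section 5, primary outcome: "Determine the effect of the in-line filter (< 5% effect or > 5% effect"), applied to ventilation, oxygen uptake, carbon dioxide output and heart rate.

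The plan does not state a multiplier for the limits of agreement, a confidence interval for the mean difference or the limits, an expected SD of the paired differences, or how an interval would be set against 5%.

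**The concern.** The study asks whether the filter changes the main exercise-test variables by less or more than 5%. The background section says that a larger effect may call for other mitigation strategies, and that the results are meant to guide other laboratories. With 10 subjects, both the mean and the SD of the paired differences are estimated loosely. A mean difference and a pair of limits shown as bare lines on a plot would look much firmer than they are.

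The one summary that the plan names does not help. The SD of the measurements within a condition mainly reflects how much men and women aged 18 to 65 differ from one another. The SD of a paired difference also depends on the correlation between a subject's two tests, which is not among the promised outputs. The paired t-test asks only whether the mean difference is zero. A P value above 0.05 does not show that the effect is below 5%.

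**Working it through.** **Inputs.** From the documents: n = 10, one filtered and one unfiltered test per subject, threshold 5%, significance level 0.05 (taken as two-sided). Assumed, because the plan is silent: 10 complete pairs with one summary value per subject, normal differences, limits at mean ± 1.96 SD, and an SD of paired percent differences of 5% (range 3-8%). The plan gives no precision figure that could be reproduced.

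**1. Precision of the mean difference.** Half-width of the 95% CI = t(9, 0.975) × SD/√n = 2.262 × SD/√10 = 0.715 SD.

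**2. Precision of a limit of agreement.** For a limit at the population mean + 1.96 population SD, the exact 95% CI comes from the noncentral t distribution with 9 degrees of freedom and noncentrality 1.96 × √10 = 6.198. Its 2.5% and 97.5% points, divided by √10, are 1.16 and 3.80. The upper limit, estimated at 1.96 SD above the mean difference, therefore has a CI from 1.16 to 3.80 SD above it. The lower limit has the mirror image.

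The usual approximation has SE = SD × √(1/10 + 1.96²/18) = 0.560 SD. This gives ± 2.262 × 0.560 = ±1.27 SD, or 0.69 to 3.23 SD. It is symmetric and understates the outer end, so the exact form is preferable at n = 10.

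**3. In percentage points.**

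| Assumed SD of differences | 95% CI half-width, mean difference | Upper limit minus mean difference | Exact 95% CI of that distance |
|---|---|---|---|
| 3% | 2.1 | 5.9 | 3.5 to 11.4 |
| 5% | 3.6 | 9.8 | 5.8 to 19.0 |
| 8% | 5.7 | 15.7 | 9.3 to 30.4 |

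If the filter's effect were judged by whether the whole CI of the mean difference lies within ±5%, an SD of 5% would require an observed mean difference within 5 − 3.6 = 1.4 points of zero. The half-width alone reaches 5 points at an SD of 5/0.715 = 7.0%.

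**4. Coverage of the limits.** The expected share of new differences inside mean ± 1.96 SD is P(|t9| < 1.96/√1.1) = P(|t9| < 1.869) = 90.6%. A simulation of one million samples of 10 agrees, and coverage is below 90% in 36% of those samples. With a multiplier of 2 the expected share is 91.1%. A factor of 2.262 × √1.1 = 2.37 gives 95% on average, but that is a prediction interval and already allows for error in the mean and the SD.

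**5. Why condition SDs are not enough.** SD of differences = √(s1² + s2² − 2 r s1 s2). The promised summary supplies s1 and s2 but not r.

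**The case against.** Bland-Altman analysis and paired t-tests are both committed to, so a mean difference and limits will presumably be reported. A reader might infer from section 8 that only means and SDs by condition will appear. The documents do not support that. Nor is paired precision necessarily lost: if 1.96-SD limits are printed, their width divided by 3.92 is the SD of the differences, and an exact paired P value with the two condition means gives the standard error. This stands. The gap is that no interval is specified, not that the paired results are withheld.

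A reader might also infer that the plan has chosen limits that are too narrow. It states no multiplier; it refers to a cited paper for the method. The 90.6% is coverage of a new difference, a prediction criterion that the plan does not adopt. As estimates of the population limits, 1.96-SD limits at n = 10 are only about 2.7% too narrow on average, since the expected sample SD is 0.973 of the true one. So 90.6% describes conventional limits and does not show an error in this plan.

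It is tempting to set the wide interval of a limit against 5% and conclude that the primary question cannot be answered. Section 5 applies 5% to the filter's effect, and nothing in the documents applies it to individual limits. The interval to compare with 5% is that of the mean difference, which is narrower.

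Finally, the plan does not fix a time point. If several work-rate stages per subject were pooled, the pairs would be clustered and none of these figures would apply as they stand. This too is a fair limit on the numbers. Pooling would not, however, add independent subjects, and it would not remove the need for intervals.

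**Conclusion.** The point holds as a gap in specification and reporting. With 10 subjects, the mean difference is known to ±0.715 SD and the distance from the mean difference to each limit to between 1.16 and 3.80 SD, yet the plan calls for neither interval. At an assumed SD of 5%, the mean difference carries ±3.6 points (2.1-5.7 for 3-8%) against a threshold of 5, so the interval can decide what the study may conclude. These sizes assume one pair per subject, complete data, normal differences and, for the limits, a 1.96 multiplier; the SD is not from the documents. The study is not invalid on this account, and the plan is not shown to use wrong limits.

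**What to change.** In section 8, replace the sentence on means and standard deviations with:

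> For each variable the mean paired percent difference (filter vs non-filter) with its 95% CI, the SD of the paired differences, and the Bland-Altman limits of agreement (one summary value per subject), each limit with its exact (noncentral-t) 95% CI, will be reported and drawn on the plot. The CI of the mean difference will be compared with 5%. Mean and SD by condition are descriptive.

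The comparison with 5% belongs to the four variables to which section 5 attaches that threshold. The plan should also state the multiplier for the limits and name the summary value taken from each test. If a 2.37-SD interval is shown instead of the limits, label it a 95% prediction interval and put no CIs around it, because it already includes the sampling error.

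The cost is one sentence and a few lines of code, with no added subjects or visits. The downside is that the agreement results will look less certain.
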